 - Staged with a planned return for reoperation (such as but not limited to damage control laparotomy or burns surgery) OR
 - Change in operative plan such that during the first procedure it is determined that a reoperation is necessary, even if the patient was enrolled preoperatively
- **Return to theatre:** Each individual patient should only be included in the study *once*. Patients returning to theatre due to complications following earlier surgery can be included, as long as their indexed procedure has not already been included in the CASCADE audit.

You should collect data on consecutive patients operated at your centre during the data collection period. This means that all eligible patients should be included.

Strategies to identify consecutive eligible patients could include:

- *Daily review of elective theatre lists.*
- *Daily review of handover sheets/ emergency admission and ward lists.*
- *Daily review of theatre logbooks (both elective and emergency).*

6. Covariates:

Data will be collected on audit standards and confounding factors for risk-adjusted analyses. These include age, sex, ethnicity, body mass index, American Society of Anaesthesiologists (ASA) grade, relevant comorbidities, smoking status, anticoagulant or antiplatelet use, preoperative blood test values, and preoperative anaemia management. Variables including operative urgency, operative procedure, operative contamination, use of tranexamic acid, intraoperative blood transfusions used, haemoglobin level at transfusion, duration of procedure and post-operative iron therapy will also be collected. Without appropriately adjusting for risk factors, it is likely that any findings would be biased and unable to be appropriately analysed on a national scale. A full list of required data fields is available in **Appendix B**, and on the REDCap database.

7. Outcome Measures and Follow-up:

Primary outcome measure:

- Rates of compliance to pre-, intra-, and postoperative audit standards in reducing risk of postoperative cardiovascular complication.

Secondary outcome measures:

- Incidence of postoperative cardiovascular complications within 30-days of surgery according to the Standardized Endpoints for Perioperative Medicine (StEP) cardiovascular.¹³ (see **Appendix D: Definitions of Key Outcomes**).
- 30-day postoperative blood transfusion rates
- 30-day complication rates defined according to the Clavien-Dindo classification (see **Appendix D: Definitions of Key Outcomes**)

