- 30-day reoperation rates
- Critical care bed days up to 30 days postoperatively
- Length of in-patient stay (days) up to 30 days postoperatively
- 30-day readmission rates
- 30-day bleeding event rates (see **Appendix D: Definitions of Key Outcomes**)
- Length of pharmacological VTE prophylaxis (days) up to 30 days postoperatively.

Follow-up should be performed in line with current routine practice within each hospital settings. No additional telephone, in-person or questionnaire-based follow-up is required. Source data may be acquired from hospital in-patient notes, clinical electronic systems, or outpatient letters.

Prior to collecting data, all collaborators will be required complete the mandatory e-learning modules available from the CASCADE project online hub:
<https://incept.ac.uk/course/view.php?id=7>

These include: (1) CASCADE Patient selection; (2) Clavien-Dindo classification (3) Postoperative cardiovascular complications; (4) Postoperative bleeding complications; (5) VTE pharmacological prophylaxis; (6) Data safety governance; (7) Quiz

8. Data Governance:

Data will be collected and stored online through a secure server running the Research Electronic Data Capture (REDCap) web application,^{27,28} and allows safe anonymised data storage by collaborators across Europe. The service is managed by the Birmingham Surgical Trials Consortium (BiSTC) REDCap system hosted at the University of Birmingham, United Kingdom. The security of the study database system is governed by the policies of the University of

Birmingham. Data management and data security within the BiSTC REDCap will abide by the requirements of the General Data Protection Regulations (GDPR) and any subsequent amendments. Collaborators will be given secure REDCap project server login details, allowing secure data storage on the REDCap system.

No patient data will be uploaded or stored on the REDCap database without prior local permissions. All data should be handled in accordance with local data governance policies, and all paper copies of any data should be destroyed as confidential waste within the centre once uploaded to REDCap. Data collected during the CASCADE study can be used for future analyses at the Study Management Group's discretion.

9. Data Analysis & Sample Size:

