Appendix B: Data Dictionary

Pre-operative Data Fields	Required data (definition / comment)	Suggested source(s)
1. Patient age	Years (whole years at the time of operation)	– Clinical letters / notes
2. Patient sex	Male / Female	– Clinical letters / notes
3. Patient body mass index (BMI)	kg/m² (record to two decimal places)	– Drug charts – Clinical letters / notes
4. Patient ASA grade	Grade I-V (Full ASA classification available at: https://www.asahq.org/resources/clinical-information/asa-physical-status-classification-system)	– Anaesthetic notes
5. Smoking status	Current (≤6 weeks, >6 weeks), Previous, Never	– Admissions clerking – Clinical notes
6. Clinical Frailty scale	1-3 / 4-6 / 7-9 (Full Clinical frailty scale available at: https://www.dal.ca/sites/gmr/our-tools/clinical-frailty-scale.html)	– Admissions clerking – Clinical notes
7. History of cardiovascular disease	Yes (myocardial infarction, angina, congestive cardiac failure, TIA/stroke, hypertension, peripheral vascular disease, atrial fibrillation, VTE, pulmonary embolism) / No If congestive cardiac failure, what is the NYHA: I / II / III / IV	– Admission clerking – Anaesthetic notes – Outpatient letters
8. History of respiratory disease	None / Dyspnoea on exertion or CXR (mild COPD) / Dyspnoea limiting exertion to <1 flight or CXR moderate COPD / Dyspnoea at rest/rate >30 at rest or CXR (fibrosis or consolidation)	
9. History of COPD	Yes / No	
10. History of chronic kidney disease	Yes (I / II / IIIA / IIIB / IV / V) / No	
11. History of liver cirrhosis	Yes / No	
12. History of diabetes mellitus	Yes - Type I / Yes - Type II (diet controlled, tablet controlled, insulin controlled) / No	
13. Active cancer and/or cancer treatment	Yes / No	
14. Inflammatory bowel disease	Yes / No	
15. Previous history of VTE	Yes / No	
16. Management of iron-deficiency anaemia	None / Preoperative iron supplementation / Tranexamic acid / RBC transfusion (If yes: 1, 2, 3, 4, ≥5 units)	
17. Preoperative treatment	Yes (Aspirin, ACEi/ARB, β-blocker, α ₂ agonist, rate controlling CCB, DHP CCB) / No If yes, was medication stopped preoperatively? (No / Yes, stopped preop only / Yes, stopped preop & postop)	– Clinical letters / notes PACS software
18. Preoperative therapeutic anticoagulation	Yes (Low Molecular Weight Heparin (LMWH), Warfarin, Direct acting oral anticoagulants (DOACs)) / No	– Clinical letters / notes PACS software

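### Section 6 names antiplatelet use as a confounder, but aspirin is the only antiplatelet the data fields can record

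*Protocol*

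**What the plan says.** Section 6 of the protocol (Covariates) opens with the purpose of the variables: "Data will be collected on audit standards and confounding factors for risk-adjusted analyses". The list that follows includes "smoking status, anticoagulant or antiplatelet use, preoperative blood test values". Antiplatelet use is named there as a class and is not limited to aspirin. The same section then states: "A full list of required data fields is available in Appendix B, and on the REDCap database".

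Two preoperative fields in Appendix B bear on this covariate:

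- Field 17 (preoperative treatment) starts "Yes (Aspirin, ACEi/ARB", continues with beta-blockers and alpha-2 agonists, and ends "rate controlling CCB, DHP CCB) / No". The only follow-up question is whether the medication was stopped.
- Field 18 (preoperative therapeutic anticoagulation) covers low molecular weight heparin and warfarin and ends "Direct acting oral anticoagulants (DOACs)) / No".

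The Appendix A form repeats both lists. It marks the treatment field as one where all applicable boxes are ticked. Neither field has an 'other' or free-text option.

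The secondary aims in section 2 include risk factors for cardiovascular complications, and the efficacy and safety of extended thromboprophylaxis. Section 7 lists "30-day bleeding event rates" as a secondary outcome.

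**The concern.** The covariate promised in section 6 cannot be built from the fields that are meant to supply it. This is not something a statistical analysis plan can repair: a plan can choose a model, but it cannot recover a drug exposure that was never collected.

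The gap is also silent. A form with no antiplatelet ticked counts as complete, so the 95% completeness rule in section 11 will not reveal it and there is no missing value to impute. The question about stopping medication is tied to the listed drugs, so interruption of any other antiplatelet is lost as well.

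At stake is the quality of adjustment in two secondary analyses, of cardiovascular risk factors and of bleeding. Section 6 itself warns that findings are likely to be biased without appropriate adjustment. For bleeding there is a further link: Appendix D counts a change in antithrombotic therapy among the criteria for clinically relevant non-major bleeding, so baseline antithrombotic treatment bears on the outcome definition.

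**Working it through.** **Step 1. Where each kind of patient is recorded**, reading section 6 against Appendix A and Appendix B fields 17-18:

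- Aspirin only: recorded as aspirin. Correct.
- Aspirin plus a second antiplatelet: recorded as aspirin. The patient is in the exposed group, but dual therapy is invisible.
- Non-aspirin antiplatelet alone, with another listed drug such as a beta-blocker: recorded as treated in field 17 through that other drug, but with no antiplatelet.
- Non-aspirin antiplatelet alone, with no other listed drug: recorded as 'None' (Appendix A) or 'No' (Appendix B).
- Anticoagulant: field 18. This field has no antiplatelet option.

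Only the third and fourth kinds of patient enter the no-antiplatelet group in error.

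**Step 2. Sample size.** Section 9 anticipates about 300 centres and ten patients per week. Each mini-team collects for 14 days. 300 × 10 × 2 = 6000, which matches the protocol's figure.

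**Step 3. Number affected.** The protocol gives no prevalence of antiplatelet use. Assume a fraction m takes a non-aspirin antiplatelet without aspirin:

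- m = 1%: 6000 × 0.01 = 60
- m = 2%: 6000 × 0.02 = 120
- m = 5%: 6000 × 0.05 = 300

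**Step 4. Dilution of the covariate's own effect.** Let a be the fraction on aspirin, p0 the event risk without an antiplatelet, and p1 the risk with one, where odds(p1) = OR × odds(p0). Non-aspirin agents are assumed to carry the same odds ratio as aspirin. The group recorded as having no antiplatelet then has risk

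pu = [(1 − a − m) × p0 + m × p1] / (1 − a),

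and the apparent odds ratio is odds(p1) / odds(pu).

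One case in full, with p0 = 0.05, OR = 2, a = 0.10, m = 0.05:

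- odds(p0) = 0.05/0.95 = 0.0526; odds(p1) = 0.1053; p1 = 0.0952
- pu = (0.85 × 0.05 + 0.05 × 0.0952)/0.90 = 0.0525; odds(pu) = 0.0554
- apparent OR = 0.1053/0.0554 = 1.90

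Over a = 10% and 20%, and p0 = 2%, 5% and 10% (all assumed):

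| True OR | m = 1% | m = 2% | m = 5% |
|---|---|---|---|
| 1.5 | 1.49 | 1.48 | 1.46 |
| 2.0 | 1.98 | 1.95-1.96 | 1.88-1.90 |
| 3.0 | 2.93-2.95 | 2.86-2.89 | 2.68-2.74 |

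The share of true users whom the recorded variable captures is a/(a + m). It runs from 0.10/0.15 = 67% (a = 10%, m = 5%) to 0.20/0.21 = 95% (a = 20%, m = 1%).

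This is an unadjusted mixture calculation. It does not measure residual confounding of other effects, or the loss from merging dual therapy with aspirin alone.

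**The case against.** The case for leaving the point out is that the mismatch is real but has little consequence.

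- **Indications are recorded.** Appendix B collects myocardial infarction, angina, TIA/stroke and peripheral vascular disease, as well as coronary angiography and ASA grade. Much of the cardiac risk that an antiplatelet drug would mark is therefore captured. This stands, with two limits: the Appendix A form omits peripheral vascular disease, and a diagnosis does not stand in for drug exposure when the outcome is bleeding.
- **Bleeding.** In the thromboprophylaxis safety analysis, the missing drug confounds only if it is also related to receiving extended prophylaxis. The protocol gives no evidence of that. The relevant audit standard ties extension to major cancer surgery, and malignancy is recorded. This stands: bias in that comparison is possible but not shown.
- **Models.** The protocol speaks only of risk-adjusted analyses and fixes no model or coding. This stands, but any coding would meet the same gap in the data.
- **REDCap.** The database is also named as a source of the field list and is not shown, so it could hold an extra item. This is weak, because section 6 presents Appendix B as holding the full list.

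A reader might infer that every patient on another antiplatelet is coded as untreated and sits in the reference group. The documents do not support that: dual-therapy patients are recorded as aspirin users, and many others will be recorded as treated through another listed drug. Nor does any figure in the protocol show that the affected patients are concentrated at the highest cardiac risk.

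**Conclusion.** The point holds as a small mismatch between a named confounder and the fields meant to measure it. The antiplatelet covariate is in effect an aspirin covariate. Patients on a non-aspirin antiplatelet without aspirin have no antiplatelet recorded, and dual therapy is indistinguishable from aspirin alone.

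The effect is confined to the secondary risk-adjusted analyses. The primary outcome is compliance with audit standards, none of which concerns antiplatelet drugs.

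If 1-5% of patients are affected, the count is 60-300 of 6000 and the dilution of the covariate's own odds ratio is modest. At a true value of 2.0 the loss is at most about 0.12 (2.00 − 1.88). These sizes rest on assumed prevalences, assumed baseline risks of 2-10%, and equal effects of aspirin and other agents. It would go too far to say that substantial confounding remains in the cardiovascular or bleeding analyses: residual confounding has not been quantified, and recorded comorbidities take up part of it.

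**What to change.** Add an 'Other antiplatelet' option to field 17 in Appendix B and to the matching list in Appendix A, with REDCap kept in step. Because Appendix A already lets collectors tick every item that applies, this one option also identifies aspirin combined with another agent, and no change of format is needed. The medication-stopped question would then cover these drugs too. The cost is one extra item to collect per patient.

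If collection can no longer change, reword the covariate in section 6 as anticoagulant or aspirin use. Then report as a limitation that other antiplatelet agents and dual therapy were not recorded. That costs a line of text.

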[name]	Consultant Anaesthetist & Honorary Senior Lecturer, London, UK	[name]
[name]	Consultant Anaesthetist & Honorary Senior Lecturer, London, UK	
[name]	Consultant Anaesthetist & Honorary Senior Lecturer, Bristol, UK	[name]
Surgeons		
[name]	Consultant Colorectal Surgeon & NIHR Clinician Scientist, Birmingham, UK	[name]
[name]	NIHR Doctoral Research Fellow, Birmingham, UK	[name]
[name]	Consultant Liver and Transplant Surgeon, Edinburgh, UK	[name]
[name]	Doctoral Research Fellow, Edinburgh, UK	[name]
[name]	Consultant Colorectal Surgeon & Honorary Senior Lecturer, Devon, UK	[name]
[name]	Consultant Colorectal Surgeon & Honorary Professor, Glasgow, UK	[name]
[name]	Consultant Colorectal Surgeon & Professor of Surgical Trials, Birmingham, UK	[name]
[name]	Consultant Vascular Surgeon & Professor of Surgery, Western Australia, Australia	[name]

Project Timeline

Dates	Description
6th Aug 2021	CASCADe Regional Lead recruitment opens
27th Aug 2021	Recruitment for CASCADe Regional Leads closes
1st Oct 2021	Online launch of CASCADe Protocol
Mid Oct 2021	Virtual conference for CASCADe Study Launch
24th Jan - 6thFeb 2022	Start of data collection period 1 (30-day follow-up ends 8 th Mar 2022)
7th Feb - 20th Feb 2022	Start of data collection period 2 (30-day follow-up ends 22 nd Mar 2022)
21st Feb - 6th Mar 2022	Start of data collection period 3 (30-day follow-up ends 5 th Apr 2022)
7th Mar - 20th Mar 2022	Start of data collection period 4 (30-day follow-up ends 19 th Apr 2022)
21st Mar - 3rd Apr 2022	Start of data collection period 5 (30-day follow-up ends 3 rd May 2022)
3rd July 2022	REDCap database locked, final data submission deadline
Mid-2022	CASCADe results presented to ESCP & AAGBI

About STARSurg

Student Audit and Research in Surgery (STARSurg) is a student-led, national research collaborative empowering medical students and junior doctors to conduct high-quality, protocol-driven audit and research in a multicentre setting. Students contribute data to national studies whilst gaining an understanding of clinical academia, audit and research methodology, and ethical considerations in research¹.

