
1. Early recognition of patients needing specialist postoperative input
	
Royal College of Anaesthetists: Guidelines for the Provision of Anaesthesia Services 2019²⁵
 
 • Provision of Postoperative Care Recommendation 3.23: Mechanisms for the early recognition of patients requiring specialist postoperative input from geriatrician-led services and/or critical care should be developed. These should include patients at risk of or presenting with delirium, multiple medical complications, functional decline or complex discharge planning.

2. Postoperative intravenous iron therapy is indicated in patients with iron deficiency anaemia
	
International consensus statement on Postoperative Anaemia after Major Surgery 2018²⁶
 
 • Postoperative iron therapy: Should postoperative iron therapy be indicated, i.v. formulations are recommended

3. Extended pharmacological VTE prophylaxis is indicated in patients at high VTE risk after major abdominal or pelvic surgery
	
National Institute of Clinical Excellence: Venous thromboembolism in over 16s: reducing the risk of hospital-acquired deep vein thrombosis or pulmonary embolism (NG89) 2018
 
 • Consider extending pharmacological VTE prophylaxis to 28 days postoperatively for people who have had major cancer surgery in the abdomen.

Methods

1. Summary

A prospective, multicentre, study will be delivered by STARSurg Collaborative & EuroSurg Collaborative across Europe. Mini-teams of up to four collaborators (medical students and at least one doctor) per speciality group per data collection period will prospectively collect data over a continuous 14-day period at each participating centre. This will be on consecutive patients undergoing major abdominal surgery, with follow-up to 30 postoperative days. All mini-teams should be supervised by a consultant in surgery.

2. Study Aims:

- **Primary Aim:** To audit compliance to pre-, intra-, and postoperative audit standards in reducing risk of postoperative cardiovascular complication.

- **Secondary Aims**
 - To characterise rates and risk factors associated with postoperative cardiovascular complications following major abdominal surgery in Europe.
 - To explore the association of pre-operative and postoperative anaemia with postoperative cardiovascular complications and short-term outcomes (length of stay, readmission and 30-day mortality).

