2. Critical care bed days (if yes)	Number (days from first post-operative day to day of discharge from critical care. If the patient has not been discharged prior to the end of 30-day follow-up, enter '31').	
3. Postoperative haemoglobin	Not applicable / Available (day 0-1, day 1-3, day 4-6, last prior to discharge) If available, please state value in grams/litre	
4. Postoperative interventions for anaemia	None / iron supplementation / Tranexamic acid / RBC transfusion (If yes: 1, 2, 3, 4, ≥5 units)	
5. Cardiovascular complications within 30 days	None / Myocardial infarction / Myocardial injury / Non-fatal cardiac arrest / Coronary revascularisation / Pulmonary embolism (symptomatic non-fatal / asymptomatic) / Deep venous thrombosis (proximal / distal; if either symptomatic / asymptomatic) / New onset Atrial fibrillation / Stroke (select all that apply) *see Appendix D for definitions Please indicate the POD of the event(s) selected.	• Clinical notes • PACS software
6. Bleeding complications within 30 days	None / Major bleeding / Clinically relevant non-major bleeding *see Appendix D for definitions	
7. Post-operative length of stay	Number (days between from the first post-operative day to day of discharge. If the patient has not been discharged prior to the end of 30-day follow-up, enter '31').	
8. Highest 30-day complication grade	None / Clavien-Dindo Grade I-V (see Appendix D for the full 7-point Clavien-Dindo scale). If grade V, was death cardiac, PE or non-cardiac? (see Appendix D for definitions)	
9. 30-day Reoperation	Yes / No	
10. 30-day Readmission	Yes - planned / Yes- unplanned / No (this applies if patient had died during initial admission) If yes: what is the grade of complication (none, grade I, grade II, grade III, grade IV, grade V)	
11. 30-day postoperative COVID status	None / Preoperative / Postoperative If preoperative: are you still symptomatic (yes/no) and were you vaccinated (no / partial / full)	
12. Haemoglobin on readmission	Not available / Available If available, please state value in grams/litre	
13. Interventions for anaemia at readmission	None / iron supplementation (Oral / Intravenous), blood transfusion (If yes: 1, 2, 3, 4, ≥5 units)	
14. Postoperative outpatient VTE prophylaxis duration	Number (days of pharmacological VTE prophylaxis the patient was discharged home with)	

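### Readmission is recorded without a day inside a window counted from surgery, so any difference in length of stay by anaemia status carries into the anaemia-readmission comparison

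*Protocol*

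**What the plan says.** - **Outcome.** Methods section 7 lists "30-day readmission rates" among the secondary outcomes, without an at-risk population.
- **Aim.** Section 2 relates pre- and postoperative anaemia to cardiovascular complications and to "short-term outcomes (length of stay, readmission and 30-day mortality").
- **Window.** Section 1 describes the cohort "with follow-up to 30 postoperative days". The Project Timeline agrees: period 1 has its last operations on 6 February and "30-day follow-up ends 8 th Mar 2022".
- **Readmission field.** Appendix B, post-operative item 10, offers "Yes - planned / Yes- unplanned / No (this applies if patient had died during initial admission"). It has no date or postoperative day and no not-applicable option.
- **Stay field.** Item 7 records postoperative stay for every patient and instructs: "If the patient has not been discharged prior to the end of 30-day follow-up, enter '31'".
- **Contrast.** Item 5, on cardiovascular complications, adds "Please indicate the POD of the event(s) selected". Item 8 classifies a death ("If grade V, was death cardiac, PE or non-cardiac") but does not date it.

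**The concern.** A readmission needs a prior discharge. With the window fixed to surgery, discharge on day 4 leaves 26 days in which a readmission can be recorded and discharge on day 25 leaves 5. A stay coded 31, or an in-hospital death, leaves none. Item 10 gives all of these patients the same answer, No, if nothing is recorded.

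The anaemia aim takes length of stay and readmission as outcomes of the same exposure, and the first mechanically limits the second. A crude readmission comparison then mixes the tendency to be readmitted with the time available to observe it. The covariates in section 6 describe patient and operative risk, not exposure time. Without the day of readmission, the timing that would separate the two cannot be recovered later.

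**Working it through.** **1. Window anchor.** From 6 February to 8 March 2022 is 22 + 8 = 30 days. The other four suggested periods also end 30 days after their last operating day. The window runs from surgery, so days at risk w = max(0, 30 − stay). The protocol states no readmission rate, so there is no other figure to reproduce.

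**2. Inputs, all assumed** because the protocol gives none:
- stay log-normal with log SD 0.75; median 5 days without anaemia, 7 or 9 with;
- readmission hazard after discharge the same whatever the stay, with cumulative hazard 0.10 over 25 days;
- either constant, h = 0.004 per day, or declining as c·exp(−t/7) with c = 0.10 / [7 × (1 − exp(−25/7))] ≈ 0.0147 per day;
- crude risk = mean of 1 − exp(−HR × H(w)), everyone in the denominator.

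**3. Individual patients, constant hazard.** Discharged on day 4: 1 − exp(−0.004 × 26) = 9.9%. Discharged on day 25: 1 − exp(−0.004 × 5) = 2.0%. The underlying hazard is the same.

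**4. No time at risk.** P(stay ≥ 30) = 1 − Φ[ln(30/median)/0.75], which is 0.8%, 2.6% and 5.4% for medians 5, 7 and 9. Mean time at risk is 23.5 days (median 5) and 21.0 days (median 7).

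**5. Crude risk ratio, anaemic v not**

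| Median stay | True HR | Constant hazard | Declining hazard |
|---|---|---|---|
| 5 v 7 | 1.0 | 8.03% / 8.93% = 0.90 | 0.96 |
| 5 v 9 | 1.0 | 7.19% / 8.93% = 0.81 | 0.91 |
| 5 v 9 | 1.3 | 9.23% / 8.93% = 1.03 | 1.16 |

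For comparison, with everyone observed for 25 days a true HR of 1.3 gives (1 − exp(−0.13)) / (1 − exp(−0.10)) = 0.1219 / 0.0952 = 1.28.

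**6. Direction.** A second set of assumptions used log SD 0.7 and a constant hazard of 10% per 30 days. With no true effect, equal medians give RR 1.00. Medians of 8 days without and 5 days with anaemia (in-hospital deaths 3% v 1%) give RR 1.20. The sign follows the stay difference.

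**7. Candidate repairs**
- *Dropping never-discharged patients only* (constant hazard, no true effect): RR 0.92 (5 v 7) and 0.84 (5 v 9). Most of the distortion remains.
- *Offset log(30 − stay) from existing fields:* under a constant hazard it works. With medians 5 v 8 and a true HR of 1.5 it returned 1.50, against 1.26 without it. Under the declining hazard it overcorrects: a null becomes 1.07 (5 v 7) or 1.13 (5 v 9), and HR 1.3 becomes 1.45 (5 v 9). It is also undefined at a stay of 30 or 31.
- *Dated readmission, time from discharge, censored at postoperative day 30* (declining hazard): about 0.99 for a null and 1.31 for a true HR of 1.3, correct within simulation error.

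**The case against.** **The protocol fixes no analysis of readmission.** A reader might infer that it counts late-discharged and still-admitted patients as fully observed. It does not say so. Section 9 sets no denominator, model or exposure time for readmission, and section 15's counterpart on roles (section 12, Authorship) assigns the analysis plan to a statistical team. Those choices may properly sit in the statistical analysis plan, which is not shown. This objection stands. It does not reach the data field: item 10 is fixed in the protocol, and no later plan can date an undated readmission.

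**Stay is already collected.** Item 7 and its code 31 identify patients never discharged and give each patient's time at risk. That also stands, and it allows a partial repair. But the repair needs an assumed hazard shape that undated data cannot check, and it can err upward.

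**The direction is not given.** A reader might infer that the association is biased downward. That requires anaemic patients to stay longer. The aim only explores associations, and the protocol reports no stay by anaemia status.

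**The stakes are modest.** The primary outcome is audit compliance. Readmission within 30 days of surgery is a coherent audit measure that matches the other 30-day outcomes. This is right for the crude rate as a description; it does not cover the comparison by anaemia status.

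**Conclusion.** The point holds as a data-field gap with a conditional consequence. Item 10 leaves readmission undated and puts patients who were never at risk under No, although item 5 already dates cardiovascular events. A crude anaemia-readmission comparison will then reflect any difference in stay.

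Under no true effect and median stays of 5 v 7 to 5 v 9 days, the crude risk ratio is 0.90 to 0.81 with a constant hazard and 0.96 to 0.91 with a declining one. These sizes rest on assumed stay distributions and hazards, and on a readmission hazard that does not itself depend on stay. That a real excess would vanish is not established: at 5 v 9, a true HR of 1.3 shows as 1.03 under the constant hazard but 1.16 under the declining one. This is a worthwhile, inexpensive improvement to one secondary aim and does not touch the primary outcome.

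**What to change.** 1. Add the postoperative day of first readmission to Appendix B item 10 and the matching Appendix A field, as item 5 does for cardiovascular events.
2. Add an option to item 10: not applicable (not discharged alive by day 30). Remove the instruction that codes in-hospital deaths as No.
3. For the anaemia aim, analyse time from discharge to first readmission among patients discharged alive, censored at postoperative day 30, with the planned risk adjustment.
4. Report the crude 30-day-from-surgery rate alongside, with its denominator stated.
5. Do not use the log(30 − stay) offset as the main analysis. If the day of readmission cannot be obtained, it could serve as a sensitivity analysis in patients with a stay below 30, with its constant-hazard assumption stated.

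**Cost.** One numeric field, one response option and a few sentences; no extra follow-up. The time-from-discharge figure is less comparable with audits that divide by all operated patients, which is why the crude rate stays. One limit remains: deaths after discharge are undated, so they cannot be handled as a competing event unless a day of death is also recorded.
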